Indicators. The therapists who will provide the neurorehabilitation programs will always be the same and will handle the same assigned patients, in the same workplace, with common materials, 1-hour sessions, 2 times a week for 6 weeks (12 sessions).

Measurement scale. Qualitative, nominal.

Dependent Variable

Hemiplegia-Hemiparesis secondary to a Cerebral Vascular Event

Conceptual definition. It is the loss of voluntary movement with alteration of muscle tone and sometimes sensation in the entire extension of one side of the body, it can be secondary to injuries, such as the cerebral vascular event that occurs in one hemisphere and affects the extremities and contralateral facial muscles. It behaves like an upper motor neuron syndrome with hypertonia, spasticity or rigidity².

Operational definition. In this work, the motor or sensorimotor disorder of the hemibody secondary to a cerebral vascular event will be verified clinically and by imaging. The usual way of evaluating the hemibody is through internationally accepted functional scales, widely validated in Spanish. For muscle tone, strength, and movement, the Ashworth and Brunnstrom scales will be used. The modified Ashworth scale allows an assessment that, although subjective, is accepted as allowing a quantitative approach. It assesses resistance to passive movement, is easy to apply, works for any joint, and has a high inter-observer reliability rate; grades muscle tone in relation to the range of motion of a joint. The Brunnstrom scale is a facilitation method that uses certain synergistic patterns of the hemiplegic patient to create movements. In this way, it seeks the immediate achievement of more coordinated and normal voluntary primitive movements, enhancing fine motor skills.

Indicators.

Modified Ashworth scale for the measurement of limb muscle tone.

Degree	
0	No increase in muscle tone
1-	Slight increase in tone manifested by minimal resistance at the end of the range of motion during a flexion or extension movement
1+	Slight increase in tone manifested by resistance in less than half the arc of movement
2	Increased pitch by more than half the range of motion, but the joint moves easily
3	Considerable increase in muscle tone with significant difficulty in joint movement
4	Stiffness in flexion or extension

Brunnstrom scale

Degree	
I	Hypotonia. There are no movements.
II	Beginning of recovery. Beginning of basic synergies, mainly through associated reactions. The hypertonia begins.

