Score	Action/ Movement	Initial valoration	Intermedia valoration	Final valoration
Sitting patient 0: no movement 9: palpable contraction 14: perform movement but not full range vs gravity 19: full range of motion vs gravity but not vs resistance 25: movement vs resistance but less than contralateral 33: normal strength	1. Shoulder abduction 2. Elbow flexion Voluntary movement of 90°			
0: no movement 11: prehension starts 19: takes the cube but is not able to hold it vs gravity 22: he takes the cube and is able to hold it vs gravity but not vs resistance 26: take the cube overcomes gravity and resistance but is less than the contralateral 33: regular clamp	3. Grasp Hand: 2.5 cm cube between thumb and other fingers.			
0: no movement 9: palpable contraction 14: perform movement but not full range vs gravity 19: full range of motion vs gravity but not vs resistance 25: movement vs resistance but less than contralateral 33: normal strength	4. Hip flexion 5. Knee extension 6. Ankle dorsiflexion			
Upper limb Index: $1+2+3+(1)/100$				
Lower limb index: $4+5+6+(1)/100$				
Total motor index: (Motor Index of UL + Motor Index of LL/2)/100				

Indicators. The application process is described in the procedures section. They will always be performed by the same doctor, who will ignore which therapy group the patient corresponds to, at the beginning, at 6 and 12 treatment sessions.

The equivalence of the results for the Motor Index is considered based on 100 total points (sum of upper limb + lower limb divided by 2).

Qualification	Equivalence
- 100 a 90 points.	Independent patients with rehabilitation for work adjustment and activities of daily living.
- 89 a 80 points.	Independent patients with limitations, who need integral rehabilitation treatment.
- 79 a 70 points.	Semi-dependent patient who needs external help and orthotics.
- 69 a 60 points.	Patients with help-dependent limitation.
- Less 60 points.	Dependent patient needs prolonged rehabilitation.

The equivalence of the results for the Fugl-Meyer scale is considered based on 100 total points, taking into account only the motor aspect of the lower and upper limb (maximum of 66 points for the upper limb + 34 points for the lower limb). The original equivalence established by the author in 1980 and the most recent one proposed by other authors are shown.

Fugl-Meyer (1980)	Duncan, Goldstein, Horner, Landsman, Samsa y Matchar (1994)
<50 = Severo	0-35 = Muy severo
50-84 = Marcado	36-55 = Severo

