Patients with a diagnosis of cerebrovascular event (CVE) will be recruited upon arrival at the PMRUcXXI in the first-time appointment area. The diagnosis will be verified and an appointment will be made to the office of one of the researchers (evaluator 1). During the appointment the purpose of the study will be explained and doubts will be clarified. Whether they accept or not, the patient will receive the consultation that is normally provided to this type of patient and the information will be recorded in the clinical record. If patient do not accept, after the consultation, the appropriate management for your condition will be prescribed and a subsequent appointment will be made with the corresponding doctor to continue the control. In case of agreeing to participate, a summary will be made in Annex 4, which includes demographic data, whether or not is a worker, the need for temporary disability for work and clinical data for the research file. The signature of the informed consent letter will be also requested (Annex 3). This physician 1 will assign the therapeutic modality by using a table of random numbers to: Group 1. Therapy supported by virtual reality; Group 2. Therapy supported by constraint-induced movement; o Group 3. Usual physical and occupational therapy. An appointment will then be made to be assessed by the second doctor (evaluator 2), who will remain blind to the treatment, and will measure the functionality of the thoracic and pelvic limbs with the different scales, described in the procedures section, including muscle tone, trophism, ranges of mobility, functionality of the limbs, as well as of the hand, coordination, balance, sensory aspects and language (Annex 2). The limb functionality scales will be applied before (initial assessment -V.I.), during (intermediate assessment -V.Int.- week 3, session 6) and after (final assessment -V.F.- week 6, session 12) of the performance of the different rehabilitation programs. At the same times, the Boston Aphasia Intensity Scale and the Intrinsic Motivational Inventory will be applied by a neuropsychologist blinded to the treatment.

Procedures.

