1. Clinical assessment and randomization. Once the patient, family member or person responsible has expressed their willingness to participate by signing the informed consent letter, they will be sent to office 16 of the outpatient rehabilitation clinic where they will be received by doctor 1 (treating) who will perform a clinical summary that will include age, sex, occupation, somatometry and the need for temporary incapacity for work, will carry out their own clinical evaluation in the way that is usually practiced in the office and will record it in the clinical file. He will be the one who monitors the patient as the treating physician and who answers all the questions that the patient, family member or person in charge may have throughout the investigation or in relation to his own condition, for which reason he will insist that he not give any information to the patient, doctor who will evaluate you later (evaluator 2) and who does not comment on aspects related to the therapy you are receiving, who reserves any doubt until the consultation. In addition, he will not know the results of the assessment using all the scales that the doctor will perform 2.

Finally, the investigator will write the corresponding information on the information capture sheet (Annex 4. Information collection sheet) and will randomly assign to the different therapeutic modalities by using a table of random numbers, which will be placed in the corresponding place of annex:

Group 1: Virtual reality

Group 2: Constraint-induced motion.

Group 3: Usual physical and occupational therapy.

When finished, the sheet will be sent to the responsible investigator, who will take the patient to physician 2 for the evaluation of the affected hemibody and date for language, then he will take him to the corresponding therapists to carry out the assigned treatment. An appointment will be made with the neuropsychologist for the evaluation of language and satisfaction.

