2. Extremity motor assessment. The patient will be admitted to consulting room 22, by appointment, where he will be received by physician 2 (blinded evaluator), who will have the indication to address the patient specifically in relation to obtaining data during the physical examination (actions to obtain the evaluation with scales). He will introduce himself and establish a rapport with the subject, but remind him that this assessment is related to an investigation and insist that he not give more information than what he requests. The evaluating physician will not know the therapeutic modality that the patient will receive. Afterwards, he will ask you to sit on the examination table and the clinical review related to the functionality of the hemibody will begin. The evaluation will begin with the motor index scale, then the quality of the fine forceps will be measured, and finally the Fugl Meyer scale. The assessment will be made before starting therapy, half the number of sessions (3 weeks) and at the end of treatment (6 weeks).

- a) **Evaluation with Fugl Meyer scale.** This scale is specific to the Cerebral Vascular Event, designed with the objective of measuring the motor deficit, balance, sensitivity and state/pain of the joints of patients who present hemiplegia/hemiparesis as a consequence of the event. In clinical practice it helps to assess the severity of the deficit, describe motor recovery, plan rehabilitation treatment and monitor the clinical evolution of patients after a stroke.

The result of this scale is measured in a numerical score, the higher numerical score corresponds to a better state of the patient's functioning. The scale is built to give ratings separately (both members, balance and sensitivity), but it can also be used globally, with a maximum of 226 points. The questionnaire must be administered by the evaluating physician, it contains 113 items encompassed in 5 domains that in turn cover three dimensions of the state of functioning and functionality in the EVC. For each item, the examiner must grant the corresponding qualifications indicated in each section.

Fugl-Meyer scale (spanish versión).

Dimension: Assessment of motor function in the upper limb.

Dominio	Item	Ini. Val.	Interm. Val	Fin. Val.
I. Osteotendinous reflexes 0: no reflexes 2: reflexes are obtained	1. Biceps 2. Triceps			

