ANNEX 4.

INFORMATION COLLECTION SHEET

Folio No.: _____

Phone: _____ Address: _____

Name: _____ Affiliation: _____

Age: _____ Sex: _____ Treatment: _____ Date: _____

Diagnosis: _____

Type of CVE: _____ Ischemic: () Hemorrhagic: ()

Affected side: Right: () Left: ()

Clinical summary:

nPPA:

Alcoholism: Yes () No () Smoking: Yes () No ()

Schooling: Yes () No () Works: Yes () No ()

Specify: _____

Requires Disability: Yes () No () Specify: _____.

PPA: DM () HTA () Other: () Specify: _____.

Neurological diseases: Yes () No () Specify: _____.

Psychiatric illnesses: Yes () No () Specify: _____.

AP: _____

Physical exploration:

Treatment group: _____

Modified Ashworth scale

Segment	Ini. Val.	Interm. Val	Fin. Val.
Superior limb			
Lower limb			

Ini.Val.= Initial valoration;

Interm.Val.= Intermedia valoration;

Fin.Val.= Final valoration

Brunnstrom scale

Segment	Ini. Val.	Interm. Val	Fin. Val.
Superior limb			
Lower limb			

Ini.Val.= Initial valoration;

Interm.Val.= Intermedia valoration;

Fin.Val.= Final valoration

Appendix 1

TABLA 13.A. Tamaño de la muestra por grupo para comparar dos medias

α unilateral = α bilateral =	0,005			0,025			0,05		
	0,01	0,05	0,10	0,05	0,10	0,20	0,05	0,10	0,20
β = E/S*	0,05	0,10	0,20	0,05	0,10	0,20	0,05	0,10	0,20
0,10	3.563	2.977	2.337	2.599	2.102	1.570	2.165	1.713	1.237
0,15	1.584	1.323	1.038	1.155	934	698	962	762	550
0,20	891	744	584	650	526	393	541	428	309
0,25	570	476	374	416	336	251	346	274	198
0,30	396	331	260	289	234	174	241	190	137
0,40	223	186	146	162	131	98	135	107	77
0,50	143	119	93	104	84	63	87	69	49
0,60	99	83	65	72	58	44	60	48	34
0,70	73	61	48	53	43	32	44	35	25
0,80	56	47	36	41	33	25	34	27	19
0,90	44	37	29	32	26	19	27	21	15
1,00	36	30	23	26	21	16	22	17	12

* E/S es el tamaño estandarizado del efecto, calculado como E (tamaño esperado del efecto) dividido por S (desviación estándar de la variable de desenlace). Para estimar el tamaño de la muestra, se busca el tamaño estandarizado del efecto y se cruza el valor encontrado con los correspondientes a los valores especificados de α y β para hallar el tamaño requerido de la muestra en cada grupo.

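### No rater is named for the Ashworth and Brunnstrom scales, and their only recording grids sit on the sheet that shows the allocation, so blind rating of these two scales is not assured

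*Combined protocol and SAP*

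**What the plan says.** - **Variables, Hemiplegia-Hemiparesis (dependent variable).** "For muscle tone, strength, and movement, the Ashworth and Brunnstrom scales will be used". Both scales are printed there as indicators. No rater, visit schedule or blinding is given for them.
- **Variables, Motor function of the thoracic limb and pelvic limb.** For Fugl-Meyer and the Motor Index the plan does name the rater: "They will always be performed by the same doctor, who will ignore which therapy group the patient corresponds to", at the start and at 6 and 12 sessions. Manual function has an equivalent statement.
- **Study General description.** Evaluator 2 is the one "who will remain blind to the treatment, and will measure the functionality of the thoracic and pelvic limbs with the different scales". The remit continues "including muscle tone, trophism, ranges of mobility, functionality of the limbs" and refers to the procedures section and Annex 2.
- **Procedures, item 2 (Extremity motor assessment).** Evaluator 2's sequence is fixed: "The evaluation will begin with the motor index scale, then the quality of the fine forceps will be measured, and finally the Fugl Meyer scale".
- **Procedures, item 1 (Clinical assessment and randomization).** At the allocation step "the investigator will write the corresponding information on the information capture sheet (Annex 4. Information collection sheet", and the assigned arm is entered on the same annex. The completed sheet then goes to the responsible investigator. Physician 1 is not to know evaluator 2's scale results.
- **Procedures, item 4.** Evaluation results are noted on Annexes 2 and 4. Who enters them is not stated.
- **Annex 4.** The grid headed "Modified Ashworth scale" and the Brunnstrom grid, for upper and lower limb at three visits, follow directly after the treatment-group line.

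**The concern.** The trial is described as single-blind, and its protection against rating bias is that evaluator 2 does not know the therapy. For the other motor scales the text says so explicitly. For the two scales that define the hemiparesis variable it does not, and the only place to write their follow-up values is a sheet carrying the allocation. The protocol itself calls the Ashworth rating subjective. If someone who knows the arm scored tone or recovery stage after treatment began, expectation could enter the comparison between arms on a listed dependent variable. A reader of the eventual report could not tell whether that had happened.

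**Working it through.** There is no figure to reproduce, since the point concerns who rates and on which form. The check sets the text against the forms.

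1. **Rater.** The section that names the scales names no rater. The section that gives evaluator 2 muscle tone names neither scale. Linking the two is a reasonable inference for Ashworth, which measures tone. It is weaker for Brunnstrom, which stages recovery.

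2. **Procedure.** The Study General description refers to the procedures section, where evaluator 2's sequence has three instruments: Motor Index, fine forceps and Fugl-Meyer. The summary at the front lists the same three. Ashworth and Brunnstrom are in neither.

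3. **Forms.** Annex 2 holds five instruments (Fugl-Meyer, Motor Index, fine clamp, Boston aphasia scale, Intrinsic Motivation Inventory) and 0 of the 2 scales in question. Annex 4 holds both: 2 scales × 2 limb segments × 3 visits = 12 cells, of which 2 × 2 × 2 = 8 are for the intermediate and final visits.

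4. **How those 8 cells could be filled.**
   - *Physician 1 rates.* The rater then knows the arm. No section assigns this task to physician 1.
   - *Evaluator 2 writes on Annex 4.* The evaluator then sees the treatment group, if it has been entered as item 1 directs. This contradicts the requirement that evaluator 2 not know the therapy.
   - *Evaluator 2 rates blind and someone transcribes.* This keeps the blind. It needs a source form that does not exist in the annexes and a transcriber who is not named. If physician 1 transcribed, the rule that physician 1 not know evaluator 2's results would be broken. If the responsible investigator did, it would not.

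   Each route therefore breaks a stated rule, assigns a task the text does not assign, or relies on a step the protocol does not describe.

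5. **Eligibility.** The inclusion criteria set a maximum Ashworth of 2 and a minimum Brunnstrom of 4. That accounts for an initial value on physician 1's sheet, but not for the intermediate and final columns.

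6. **Would Annex 2 be a safe home for the grids?** Not as drawn. Its motor-scale header has a group field, and four of its five instruments (all but Fugl-Meyer) have one block of columns per arm. A rater using those grids would see or reveal the arm by choosing a column.

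**The case against.** The strongest case against the point is that a grid's position on a form does not show who does the rating. Annex 4 passes to the responsible investigator after allocation, and item 4 treats it as a capture sheet, so blind rating with later transcription is consistent with the text. The remit given to evaluator 2 is also loose: it includes trophism, for which Annex 2 has no grid either, so it cannot be read as a precise assignment of scales. The protocol credits Ashworth with high agreement between observers as well as calling it subjective. The hypothesis and sample size use Fugl-Meyer, which is explicitly rated blind.

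Most of this stands, and it limits the conclusion. A reader might infer that tone and recovery stage will be rated unblinded by the treating physician. The documents do not support that, because no section gives follow-up scoring to physician 1. A reader might also want an inflated error rate from an assumed rater shift. Any such figure would only restate the assumption: the documents give no shift, the scales are ordinal grades, and the comparison has three arms.

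The objection does not remove the gap. Agreement between observers is no protection against an expectation that comes from knowing the arm. The transcription route that would preserve blinding is nowhere described.

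**Conclusion.** The mismatch between text and forms is real. The supported conclusion is that the rater of Ashworth and Brunnstrom is unspecified and that blind follow-up rating is not assured. It is not shown that the ratings will be unblinded.

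The reach is limited to these two scales: 8 follow-up cells per patient on a sheet that shows the allocation. The Fugl-Meyer hypothesis and the sample size are untouched. The Statistic analysis section names no individual scale, so the role of Ashworth and Brunnstrom in the comparison between arms is itself not stated. No size of bias can be derived. The conclusion assumes that the annexes as printed are the forms in use and that the group entries are completed before the follow-up visits. Item 1 directs this for Annex 4; nothing says when the Annex 2 group field is filled in.

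The point should be corrected because the remedy is cheap and the text already intends blind assessment.

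**What to change.** - Name evaluator 2 as rater of both scales at the initial, intermediate and final visits, in the Hemiplegia-Hemiparesis variable, and add both to the sequence in Procedures, item 2.
- Record them on an evaluator form with no group field and no arm-labelled columns. Remove the group field and the per-arm column blocks from every Annex 2 form used by a blinded rater, including those of the neuropsychologist. Moving the grids to Annex 2 unchanged would not be enough.
- On Annex 4 keep only the entry values needed for the inclusion criterion, labelled as screening values and not used as outcomes.
- State in Procedures, item 4 who transfers results from the rating forms to the capture sheet.
- Reconcile the Hemiplegia-Hemiparesis variable, the Study General description and Procedures items 1, 2 and 4 with Annexes 2 and 4.

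The cost is a form re-layout, a few lines of text and a few minutes of evaluator 2's time per visit. No extra staff are needed.
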